6. STUDY INTERVENTIONS

Interventions, Administration, and Study Duration:

All study interventions done in this trial are standard of care procedures for cerebral vasospasm treatment. After obtaining informed consent, a clinical examination will be done to assess patient's neurological status pre-infusion. The patient will be taken to the Interventional Radiology suite where he/she will be assigned to one of the three treatment groups based on the center specific randomization scheme for endovascular intra-arterial drug infusion.

Infusions can be given for a total of two times during the same procedure time slot. A post-infusion angiogram will be done minimally10 minutes after the treatment to check for improvement in the spasmic blood vessel. Balloon angioplasty can be performed if the post-treatment angiogram run shows insufficient improvement as per the treating physician's discretion. Post-infusion clinical status will be noted. Three months post-discharge from hospital, study participants will be followed up in clinic to evaluate their functional clinical outcome. If, for any reason, the patient cannot come back for a follow-up visit, the PI/Co-PI's will contact the patient via phone/email to gather the required data. A minimum of mRS and NIHSS should be gathered for follow-up data.

Handling of Study Interventions:

Each participating study center will use its available hospital pharmacy services to acquire the drugs to be used in the study as per their current standard procedures. The study coordinator at each site will maintain a log for study randomization, enrollment and withdrawal.

Concomitant Interventions:

Table 1

Balloon angioplasty can be done if the drugs used fail to improve the spasm in the blood vessels. The vessel diameter will still be recorded at the end of the study.

7. CLINICAL AND LABORATORY EVALUATIONS

For this clinical trial no additional clinical or laboratory evaluations are required apart from the standard hospital routine care procedures. The required evaluations are listed below: Schedule of Evaluations

Table 1.			-	
Evaluation	Screening	Pre-	Post –	3 months
	_	Vasospasm	Vasospasm	Follow up
		Treatment	Treatment	1
Informed Consent	Y			
Pregnancy Test	Y			
Clinical examination mRS, NIHSS, (24-hr window)	Y	Y	Y	Y
NON-contrast CT scan (24-hr window)	Y	Y	Y	Y
TCD (Lindegaard Index)	Y	Y	Y	
Pharmacological angioplasty	Intervention			

Balloon angioplasty	Concomitant intervention			
Intracranial pressure	Y Y		Y	
Enter Clinical DATA in REDCAP	ENTER within 1 week of discharge & F/U			

Time Frame:

Pre-vasospasm treatment: 24 hours prior to procedure

Post-vasospasm treatment: within 24 hours of the procedure

3-month follow-up visit: +/- 2 weeks

Core Lab Image upload: Please upload all angiogram and CT scan images of the patients enrolled each month to the core lab website by the 7th calendar day of the preceding month.

Evaluations:

Screening & Pre-entry: Screening & pre-entry evaluations may occur simultaneously. Any patient who presents with cerebral vasospasm within 3-21 days after aneurysmal SAH and has an intervention done for aneurysm rupture is eligible for this clinical trial assuming other inclusion criteria are met.

Entry: On confirming patient eligibility and informed consent process, the patient will be randomly assigned to one of the three treatment groups for intra-arterial infusion of study drugs.

On-Study/On-Intervention Evaluations: Pharmacological angioplasty

Intervention Discontinuation Evaluations: If for any reason the PI or the Co-PI discontinue the intervention on a patient, the data will still be collected and entered into the data sheet; patients will still receive all medical & surgical care they need as per routine hospital care procedures. During analysis data from discontinued participants will be factored in.

- On Study/Off-Intervention Evaluations: Before discharge from hospital after intervention, patient's neurological status will be noted using Modified Rankin scale and NIH Stroke Scale [NIHSS]. Any new changes on CT scan should be noted, ICP should be noted, and any procedure complications or delayed procedure complications should be noted.
- Off-Study Requirements: Study participants will be followed up in clinic at 3 months post-discharge from hospital. All participants will receive this follow-up visit, even if the study intervention was discontinued.

Informed Consent: Informed consent process will take place in a private room where the PI/Co-PI and or the study coordinator will explain the study trial and enrollment process to the potential participants. They will be given ample time to understand the study and to be asked if they have any questions or concerns.

The Informed Consent form is attached in the appendix below.

Documentation of vasospasm: By clinical symptoms, transcranial doppler ultrasound, CT-angiogram & cerebral angiogram.

Clinical Assessments: A complete neurological examination will be done & Modified Rankin score (mRS), NIHSS will be noted. At 3-month follow-up appointment, there will be a recording taken during the mRS evaluation. This recording will contain only the Subject ID and the mRS questions and answers.

8. MANAGEMENT OF ADVERSE EVENTS

This protocol presents minimal risks to the subjects, and adverse events or other problems apart from those expected during standard hospital care for this condition are not anticipated.

In the unlikely event that such events occur, serious and unanticipated and related adverse events or unanticipated problems involving risks to subjects or others will be reported in writing within 48 hours to the institutional review board of the institution involved [IRB], using the current procedures followed at each participating center. The primary site should also be informed of such an event within 48 hours. All appropriate funding and regulatory agencies will be notified there after by the study coordinator The investigator will apprise fellow investigators and study personnel of all adverse events that occur during the conduct of this research project via email as they are reviewed by the principal investigator. The protocol's research monitor(s), e.g., study sponsors, funding and regulatory agencies, and regulatory and decision-making bodies will be informed of serious adverse events within 5 days of the event becoming known to the principal investigator:

Adverse effects of cerebral angiogram: BLEEDING FROM GROIN FEMORAL ARTERY OCCLUSION STROKE SYMPTOMS (SLURRED SPEECH, WEAKNESS AND/OR LOSS OF SENSATION IN FACE, ARMS & LEGS) ALLERGIC REACTION TO CONTRAST AGENT KIDNEY DAMAGE SEVERE HEADACHE

Details of adverse events, management & monitoring plan for adverse events is listed in appendices

9. CRITERIA FOR INTERVENTION DISCONTINUATION

The PI & Co-PI can discontinue study intervention(s) based on their clinical judgment & patient's best interest. All the data that needs to be entered in the Case Report Form (CRF) will be collected and data from discontinued study participants will be factored in in the analysis.

10. STATISTICAL CONSIDERATIONS

Design:

The clinical trial will be conducted under a common umbrella protocol developed by the primary site (UTH) with the intention of combining data from all satellite centers for analysis. Each investigational site will give utmost importance to follow the study protocol to maintain consistency in study execution at all centers. Patients will be randomly assigned to 3 treatment groups in a 1:1:1 allocation ratio. The three therapeutic regimens to be considered are:

Group 1: nicardipine (Cardene) 5 mg per circulation in 25 mL of 5% Dextrose,

Group 2: verapamil 10 mg per circulation in 10 mL saline

Group 3: Cocktail agents: 5 mg in 25 mL 5% Dextrose + verapamil 10 mg in 10 mL saline + nitroglycerin 200 mcg in 4 cc of D5W per circulation.

A maximum of 330 subjects, 110 per treatment arm, will be randomized. The trial includes interim analyses that may reduce the maximal sample size if clear differences emerge among the arms during the conduct of the trial.

Interim Analyses:

Interim analyses will be performed to allow for discontinuing enrollment to treatment arms due to futility. After approximately 90 subjects have been randomized, 30 per arm, interim analyses will begin at the next quarterly Data and Safety Monitoring Board (DSMB) meeting. Subsequent interim analyses will be performed to coincide with DSMB meetings, which will occur after 40 subjects, 70 subjects, 110 subjects, 165 subjects, and 248 subjects have completed the study, and at the conclusion of the study (330 subjects).

At each interim analysis, an Analysis of Variance (ANOVA) will be performed to compare the PIIR results across treatment arms. If the overall treatment effect is significant with a p-value<0.05, then pairwise treatment comparisons will be performed. If any pairwise comparison is significant at a Tukey's adjusted two-sided p-value of 0.02 (p< 0.02), the poor performing arm will be dropped from the randomization scheme. If multiple arms are dropped and only one treatment arm remains open for randomization, that arm will be declared as best, and the clinical trial will end. Pairwise comparisons will only be performed if the overall treatment effect in the ANOVA is significant.

A maximum of 110 subjects will be randomized to each treatment arm, for a total sample size of 330. If an arm or arms are dropped early, the final sample size will be less than 330. For example, suppose an interim analysis is performed after 70 subjects are randomized to the 3 treatment arms (total sample size 210). Suppose further, at the interim analysis one arm is dropped, and the remaining two arms continue to enroll to completion. The final sample size will be 290, i.e., 70 subjects in the dropped treatment arm, and 110 in each of the remaining treatment arms.

Enrollment will continue while the interim analyses are performed

Final Analyses:

All patients will be included in analyses utilizing the Intent-to-Treat approach that includes all subjects randomized in their randomized treatment arm regardless of treatment received.

At the final analysis, the primary outcome measure, PIIR will be compared between treatment arms using an ANOVA model. All data will be used in the final analysis, including any arms that may have been dropped from the randomization. If the overall treatment effect in the ANOVA model is significant at the two-sided, 5% level, then pairwise comparisons among treatment arms will be conducted using Tukey's adjusted p-values with p<0.0330 declared as statistically significant. This value controls global type I error (mistakenly claiming any pairwise difference when all treatments are equal) accounting for 6 interim analyses at the anticipated accrual rate of 2 years. If accrual significantly deviates from the anticipated accrual rate, further trial simulations will be conducted to determine an appropriate adjustment for the actual number of interim analyses conducted.

Descriptive statistics, means, medians, and standard deviations, will be reported for PIIR in each treatment arm. The two-sided 95% confidence interval will also be presented for the PIIR in each treatment arm.

The key secondary outcome, mRS (Modified Rankin Scale) at 3-months post-treatment, will be summarized by treatment arm by reporting the counts and proportions in each mRS category. Comparisons among treatment groups will be made using a Chi-square test.

Additional secondary outcomes include SAE (severe adverse event) occurrences and the rate of treatment failure with balloon angioplasty. These outcomes will be summarized descriptively by presenting rates and proportions. Exploratory analyses comparing outcomes between treatment arms will be made using a Chi-square test.

Additional exploratory multivariable linear regression models will be created for the PIIR outcome, adjusting for treatment groups and additional baseline factors.

The analyses for the secondary outcomes are considered exploratory and no adjustments for the multiple tests and multiple comparisons will be made. Results will be interpreted cautiously understanding the some results may be significant at the 5% level due to chance alone.

Sample Size Justification:

Simulations were performed to estimate the power of the study for the primary outcome measure, PIIR, with a maximum sample size of 330 (110 per treatment arm) and the interim analyses for possible early arm dropping. A range of scenarios of PIIR were examined; the key scenarios used to power the trial are presented in Table 2.

Table 2.

Scenario	Treatment Arm 1: Nicardipine (N)	Treatment Arm 2: Verapamil (V)	Treatment Arm 3: Combination (C)
Combo 20	0.10	0.10	0.30
Mixed 1530	0.10	0.15	0.30

Note that the scenarios are both in favor of Verapamil over Nicardipine, but the results are symmetric if Nicardipine and Verapamil were reversed.

The trial will make every pairwise comparison:

- N versus V
- N versus C
- V versus C

The simulations focused on the V>N, C>N, and C>V comparisons. The following table presents the expected (mean) sample size and probability that the combination treatment regimen is better than the verapamil regimen, i.e., Pr(C>V), the main comparison of interest. Power is defined as the probability of identifying the superiority of the best dose over the other two doses.

Table 3.

Scenario	Expected N	Power Pr(C>V)
Combo 20	177	0.95
Mixed 1530	211	0.77

Table 3 demonstrates, that for a hypothesized scenario of "Combo 20" where the combination therapy PIIR is 0.30 compared to 0.10 in Nicardipine and Verapamil, the study will have over 90% power and an expected sample size of 177. Both the Nicardipine and Verapamil arms would have been dropped at interim analyses before they reached their maximum enrollment of 110. If the scenario of "Mixed 1530" is observed, a situation where the Nicardipine arm PIIR is 0.10, the Verapamil arm PIIR is 0.15 and the combination arm is 0.30, the study will have 77% power and an expected sample size of 211. Again, both the Nicardipine and Verapamil arms would have been dropped at interim analyses before they reached their maximum enrollment of 110.

Missing Data and Dropout Rate: We do not anticipate missing data for the primary outcome PIIR as the angiogram will be performed 10 minutes post-infusion. For the secondary outcome, mRS at 3-months, based on previous studies, we estimate up to a 20% loss follow-up. Efforts will be made to keep all patients in the study through the 3-month follow-up visit. Substantial efforts will be made to ensure complete follow-up. Rates of missing data and loss to follow-up will be reported by treatment arm. We will attempt to document maximum amount of information regarding the status of these

patients who drop out. This procedure will help to compare characteristics of those patients who completed the study with those who did not.

Data and Safety Monitoring:

In order to ensure patient safety and integrity of data collection, data and safety monitoring during this trial will include both internal and external mechanisms. The PI has developed an internal monitoring system, which will be implemented after each enrolled patient and on a monthly basis at the host site, University of Texas Health Science Center Houston. The study team will perform internal monitoring. In addition, on a yearly basis, a monitor will be asked to review study and safety data for all participating centers. Monitoring of participating centers will occur on a yearly basis, or following the completion of the study for each additional two subjects at each center, whichever occurs first. Monitoring may occur in person, or remote. Lastly, the Data and Safety Monitoring Board will independently review the accumulating data, assess the risk to benefit ratio, and can consider halting the trial if the risk to benefit ratio is deemed unacceptable. The external monitor and the DSMB will also monitor protocol compliance, safety, and onschedule study progress.

11. DATA COLLECTION, SITE MONITORING AND ADVERSE EVENT REPORTING

Data collection: detailed clinical information will be gathered using an established method approved by UT Health for abstracting information from electronic database and by the approved established method at each participating site.

Each participating center will use REDCap data software an online secure web application to enter the data in the central REDCap database managed by UT-Houston.

All the radiographic images will be evaluated and analyzed by a single CORE LAB (at The University of California – Los Angeles) centrally in blind fashion. The radiographic images will be submitted via VPN with security and with federal Health Insurance Portability and Accountability Act (HIPPA) compliance.

The patient's demographics (gender, age, race, BMI, co-morbidity, tobacco use, cocaine/illicit drug use history), aneurysm treatment modality, days after the SAH and aneurysm treatment, vasodilator(s) used (Group #) and numbers of the treatment sessions will be submitted via REDCap. Summaries will be provided quarterly to the DSMB members.

Records to Be Kept: All patient data will be de-identified and CRFs will be stored on password protected cloud drive

Data and Safety Monitoring Plan & Quality Assurance:

The Data and Safety Monitoring Board (DSMB) is responsible for conducting on going safety reviews of the trial. The first meeting will be held when approximately 40 subjects have completed the study and subsequent meetings will be held at following each of the following study timepoints, or every 6 months, whichever occurs first.

- 70 subjects completed the study
- 110 subjects completed the study
- 165 subjects completed the study
- 248 subjects completed the study
- 330 subjects completed the study

(Subject completion of the study will be defined as a subject having a completed 90-day follow up and completed analysis of study imaging by the corelab)

Frequency of the meetings may be changed by the Chair based on need. Meetings may be in person, via teleconference, or a combination of the two. A quorum must occur for the meeting to proceed.

During the review process the DSMB will evaluate whether the study should continue unchanged, require modification/amendment or be closed to enrollment and will inform the trial co-PIs of the study.

The trial co-PIs are responsible for communicating with DSMB at each time point listed above regarding potential safety issues and whether the study should continue unchanged,

require modification/amendment, or be closed to enrollment. These will be further communicated with the individual participating local PIs.

The principal investigator or the Institutional Review Board (IRB) have the authority to stop or suspend the study or require modifications.

Data Safety Monitoring Board

[name]; [name]. [name]

12. HUMAN SUBJECTS

Institutional Review Board (IRB) Review and Informed Consent:

This protocol, the informed consent document and any subsequent modifications will be reviewed and approved by the IRB or ethics committee responsible for oversight of the study. A signed consent form will be obtained from the subject. For subjects who cannot consent for themselves, such as those below the legal age, a parent, legal guardian, or person with power of attorney, must sign the consent form; additionally, the subject's assent must also be obtained if he or she is able to understand the nature, significance, and risks associated with the study. The consent form will describe the purpose of the study, the procedures to be followed, and the risks and benefits of participation. A copy of the consent form will be given to the subject, parent, or legal guardian, and this fact will be documented in the subject's record.

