1. SYNOPSIS

Study Title: The Intra-arterial Vasospasm Trial - A Multicenter Randomized Study

Objectives: The primary objective of the study is to determine the optimal intra-arterial drug treatment regimen for arterial lumen restoration after cerebral vasospasm following aneurysmal subarachnoid hemorrhage.

The secondary objective is to evaluate clinical outcome 90 days after patient discharge following in-hospital optimal intra-arterial drug treatment for cerebral vasospasm.

Design: This study is a prospective multicenter randomized trial.

Outcome variables: The primary outcome measure is the post-infusion improvement ratio (PIIR) assessed 10 minutes after completion of the intra-arterial infusion. PIIR is a measure of arterial lumen diameter pre- and post-intra-arterial drug infusion in the presenting vasospasmic blood vessel.

Modified Rankin Scale (mRS) at 3 months post-hospital discharge will be recorded as a secondary outcome to assess overall clinical outcome.

Interventions: The interventions in this study are part of the routine standard of care (SOC) procedures for cerebral vasospasm treatment. Following surgical or endovascular intervention for aneurysmal subarachnoid hemorrhage (aSAH) if patients develop cerebral vasospasm refractory to maximal medical management, endovascular treatment by intra-arterial drug infusion of a single drug agent or a cocktail of drug agents will be initiated.

Study participants will be randomly assigned to one of the three treatment groups where one single drug agent or a cocktail of drug agents will be intra-arterially administered. *Group 1* will be treated with nicardipine. *Group 2* will be treated with verapamil and *Group 3* will be treated with the combination of verapamil, nitroglycerin and nicardipine. Pre- and post-infusion vasospasmic vessel diameters will be compared. The change in diameter will be quantified based on the mean percentage change. At three months post-hospital discharge, study participants will be followed up in clinic to evaluate clinical outcomes.

Duration: The total duration for study participation required is the standard hospital stay for postaSAH vasospasm treatment and one follow-up clinic visit at 3 months following hospital discharge.

Sample Size: The study will require a maximum of 330 patients, 110 in each of the three treatment regimens. Subjects will be randomized equally into one of three treatment groups.

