If any drug related complications occur the medications will be stopped immediately. The following conditions would warrant for immediate stopping of the study drug: Marked hypotension, bradycardia, severe tachycardia, high degree AV-block, asystole, crescendo angina & methemoglobinemia

A protocol deviation is defined as any study action taken by the investigator or site personnel in conflict with the study protocol. The investigator and/or sponsor will characterize deviation severity as per the following Table.

Deviation severity	Definition
Major deviation:	Any deviation from subject inclusion and
	exclusion criteria, subject informed consent
	procedures or unauthorized drug use.
Minor deviation:	Deviation from a protocol requirement such
	as incomplete/inadequate subject testing
	procedures, follow-ups performed outside
	specified time windows, etc.

Investigators must notify the Study Chairs & respective IRB within 24 hours if a deviation is required to protect subject safety. The Study Chairs may terminate investigators and/or investigative sites from the study if the rate of protocol deviations is deemed high or patient safety is in question.

During the DSMB reviews, occurring every 6 months at a minimum, the DSMB members will review all serious related AE's (catheter induced spasm, new ischemic stroke, hemiplegia, aphasia, visual impairment or blindness, Intra cranial artery tear) to adjudicate if the SAE's are procedure related, drug related or other. The DSMB members may terminate investigators and/or investigative sites from the study if the rate of protocol deviations is deemed high or patient safety is in question.

IV. STUDY FLOW CHART

IRB NUMBER: HSC-MS-13-0586 UTHealth IRB APPROVAL DATE: 11/09/2021

V. DRUG DOSE TABULATION

NICARDIPINE		
Drug Label suggested	Maximum dose of 15 mg/hour (0.25 mg/minute)	Reference: page 6 of
dose	Until desired blood pressure reduction is achieved.	package insert
Drug Label suggested	75 mL/hour (1.25 mL/minute)	Reference: page 7 of
infusion rate	Concentration: 0.2 mg/mL	package insert
Revised drug dose per infusion	5 mg in 25 mL 5% Dextrose Infused at the rate of 1.25 mL/ minute (i.e. 0.25 mg 20 minutes	/minute) over a period of

VERAPAMIL		
Drug Label suggested	Initial dose: 5-10mg/2minutes (2.5-5 mg/minute)	Reference: page 7 of
dose	Repeat dose: 10mg, 30 minutes after the first dose if	package insert
	initial response not adequate.	
Drug Label suggested	2.5 - 5mg/minute	Reference: page 8 of

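### The arm-dropping looks have two different starts, a completion trigger that can push the last look past enrolment, no stated data cut, and an unconditional claim about dropped arms

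*Combined protocol and SAP*

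**What the plan says.** **Start.** Section 10, Interim Analyses: "After approximately 90 subjects have been randomized, 30 per arm, interim analyses will begin at the next quarterly" DSMB meeting. Later looks coincide with DSMB meetings, "which will occur after 40 subjects, 70 subjects, 110 subjects, 165 subjects, and 248 subjects have completed the study", and with the end of the study at 330. Section 11, Data and Safety Monitoring Plan: "The first meeting will be held when approximately 40 subjects have completed the study". Later meetings follow at the same counts "or every 6 months, whichever occurs first". Appendix III, Monitoring Plan: "During the DSMB reviews, occurring every 6 months at a minimum".

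**Counting unit.** Section 11: "Subject completion of the study will be defined as a subject having a completed 90-day follow up and completed analysis of study imaging" by the core laboratory.

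**Endpoint.** The dropping test (ANOVA at 0.05, then Tukey-adjusted 0.02) uses PIIR only. The Synopsis defines the primary outcome as the "post-infusion improvement ratio (PIIR) assessed 10 minutes after completion of the intra-arterial infusion". Enrolment continues while a look is carried out.

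**Data cut.** Section 10 compares PIIR across arms at each look and does not say which patients contribute. Its worked example counts a look in randomised patients (70 per arm, 210 in total).

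**Loss.** For the 3-month mRS, Section 10 says "we estimate up to a 20% loss follow-up".

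**Claimed result.** Table 3 gives expected N and power of 177 and 0.95 (Combo 20) and 211 and 0.77 (Mixed 1530). The text below it states, with no probability attached, that in both scenarios both single-agent arms are dropped at interim before reaching 110.

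**The concern.** The looks exist to stop randomising patients to a worse arm. Three matters that govern how well they do so are open or poorly matched to that purpose.

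- The start is given in two units at two kinds of meeting. No section says whether a 6-monthly meeting carries the dropping test, although the final threshold of 0.0330 assumes six interim analyses.
- Each milestone waits for 90-day data that play no part in the test, and loss to follow-up delays it further.
- The data cut is unstated, and expected sample size depends on it far more than on any other open detail.

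Separately, a reader of Section 10 would conclude that early closure of both single-agent arms is certain in the two planning scenarios. At stake are patient exposure and a rule the DSMB can apply in only one way.

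**Working it through.** **Inputs.** Maximum 330, 110 per arm, 1:1:1 (Section 10). Enrolment of 18 months (Synopsis) or 2 years (Section 10, Final Analyses); both are used. Follow-up of 3 months, with hospital stay and read time set to zero (either would make completer looks later). Loss of 0 to 20%. Scenario means from Table 2. The simulation SD of PIIR is not stated; Section 3 gives only 36.6 and 12.0 percentage points from the retrospective study. An SD of 0.34 is assumed because it gives power close to Table 3.

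**1. Table 3.** The stated rules were simulated with looks at 90 randomised and then quarterly, 24-month accrual and every PIIR used (expected N / power):

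| SD (assumed) | Combo 20 | Mixed 1530 |
|---|---|---|
| Table 3 | 177 / 0.95 | 211 / 0.77 |
| 0.34 | 176 / 0.951 | 209 / 0.788 |
| 0.345 | 179 / 0.944 | 212 / 0.777 |
| 0.366 | 194 / 0.90 | 225 / 0.70 |

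Table 3 is attainable, but only with an SD that the plan does not give.

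**2. Start of the looks.** Accrual is 330/24 = 13.75 or 330/18 = 18.33 per month.
- 90 randomised: 90/13.75 = month 6.5, or 90/18.33 = month 4.9. Waiting up to a quarter for the meeting gives 90-131 or 90-145 randomised.
- 40 completers: 40/13.75 + 3 = month 5.9 (81 randomised), or 50/13.75 + 3 = month 6.6 (91) at 20% loss. With 18-month accrual, month 5.2 (95) to 5.7 (105).

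The two starts are close, but their order is not determined.

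**3. Last look (all three arms open).**
- No loss: 248 + 3 x 13.75 = 289 randomised, or 248 + 3 x 18.33 = 303. That leaves 41 or 27 to enrol.
- 20% loss: 248/0.8 = 310 must be followed. 310/13.75 + 3 = month 25.5 against closure at 24; 310/18.33 + 3 = month 19.9 against closure at 18.
- Loss at which the look reaches closure: 1 - 248/(21 x 13.75) = 14.1%, or 1 - 248/(15 x 18.33) = 9.8%.
- The 6-month rule does not rescue it. At 20% loss, 165 completers fall at 206.25/13.75 + 3 = month 18.0, and six months later is month 24.0, when enrolment closes. With 18-month accrual they fall at month 14.25, and 14.25 + 6 = 20.25 is past closure.
- 330 x 0.8 = 264, so 330 completers cannot be reached at that loss.

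**4. Data cut.** Expected N, Combo 20 / Mixed 1530, SD 0.34, across the readings of the schedule and both accrual rates:

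| Loss | Every PIIR on hand | Completers only |
|---|---|---|
| 0% | 177-192 / 213-224 | 217-230 / 245-255 |
| 20% | 179-192 / 215-226 | 241-251 / 263-272 |

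For SD 0.32-0.36 (completer milestones, 24 months, no loss) the ranges are 164-190 / 203-225 on hand and 210-228 / 235-252 for completers only. Completers only stays above Table 3 throughout. Power for the combination over both arms is 0.94-0.96 / 0.78-0.80 in every SD 0.34 cell.

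**5. Both single-agent arms dropped.** Dropping both makes the combination the declared best arm. Section 10 defines power as showing the best arm superior to the other two, so the probability of dropping both cannot materially exceed 0.77 in Mixed 1530 or 0.95 in Combo 20. Counting drops made while enrolment is open, simulation gives about 55-65% in Mixed 1530 and 77-85% in Combo 20 with every PIIR on hand; with completers only, 32-48% and 52-69%. The highest Mixed 1530 figure on the schedule of step 1 at SD 0.34 is 0.73, when looks after enrolment has ended are counted too.

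**6. Null error with 0.0330.** About 0.04-0.05 if only a final pairwise claim or a declared best arm counts (0.057 at most in one set of runs), and about 0.06-0.09 if any interim drop counts as a claimed difference.

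**The case against.** Much can be said for the plan, and several stronger readings fail.

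- *A reader might infer that the schedules contradict each other throughout.* They do not. The completer counts are identical in Sections 10 and 11. Six-monthly is a minimum that quarterly meetings satisfy, and the DSMB Chair may change the frequency. Six interim analyses fits one look at 90 plus five completer looks. Only the start, and which meetings carry the test, are unresolved.
- *A reader might infer that looks will use completers' PIIR only, so that expected N is well above Table 3.* No section says so. The worked example counts randomised patients, and Table 3 matches the on-hand reading. The larger figures show why the cut must be written down; they are not a forecast.
- *A reader might infer that every look is late by a full follow-up period (41 or 55 patients).* That compares 40 completers with 40 randomised. The plan means to start near 90 randomised, which is about where 40 completers falls. The real timing problem is the last look.
- *A reader might infer that the trial cannot finish at 20% loss.* The final analysis uses all randomised patients, so the 330-completer point is then only a label. Phone or email follow-up (Section 6) may also keep loss lower.
- *A reader might infer that Table 3 gives no support for early closure of both arms.* It gives some. If at most one arm is dropped, the other two run to 2 x 110 = 220, so an expected N of 177 or 211 requires that some trials drop both.

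A DSMB may also reasonably want 90-day outcomes before an arm closes. That supports reviewing them at the meeting, but does not require them as the trigger for a PIIR test.

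**Conclusion.** The point holds as a should-fix matter of specification and patient exposure. The start of the looks is stated in two ways, and no section says which meetings carry the test. Tying the looks to 90-day completion makes the 248-completer look useless for sparing patients once loss exceeds about 14% (24-month enrolment) or 10% (18-month), both inside the plan's own 20% bound. The data cut is unstated. The documents point to every PIIR on hand, under which Table 3 roughly holds; under completers only it would not. The sentence that both single-agent arms are dropped is wrong as unconditional wording: in Mixed 1530 at least about 1 - 0.77 = 23% of trials would not drop both.

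The timing results need only accrual arithmetic and the assumed constant rate. The expected-N and drop figures rest on the assumed SD of 0.34, normal PIIR and equal SDs. A reader might infer that power or type I error is broken. Power is essentially unchanged. Whether 0.0330 holds the error near 5% depends on whether an interim drop is a claimed difference, which the plan does not say, so neither conclusion is supported.

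**What to change.** 1. Reconcile Section 10, Section 11 and Appendix III into one look schedule. State that each look analyses every core-lab PIIR read on hand, and say which DSMB meetings carry the dropping test. Trigger at least the last look on PIIR reads so that it falls inside enrolment. Keep 90-day data for the DSMB's safety review. Six looks at 90, 131, 172, 214, 255 and 296 reads are one example only. They give expected N of 178 / 210-213 with current reads and 191-195 / 223-228 with an assumed one-month read lag, so they save little against milestone looks that use every PIIR on hand.
2. Confirm Table 3 and 0.0330 by simulation under the chosen schedule, stating the SD, the read lag and whether an interim drop counts as a claimed difference. Section 10 already foresees re-simulation if accrual deviates.
3. Replace the unconditional sentence after Table 3 with the simulated probability of dropping both arms in each scenario.

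**Cost.** Wording changes and one simulation exercise. Core-lab reads must be current at each look; Section 7 sets monthly image upload but no read time. The most recent patients' 90-day outcomes will not be known when an arm is dropped.
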